After enrollment, patients will undergo endo-rectal, multi-parametric 1.5 Tesla MRI with Dynamic contrast enhancement and Diffusion Weighted images. Areas on MRI that have a high level of suspicion for prostate cancer will be identified (right or left, Central or peripheral gland) and categorized from 1 Negative to 5 highly suspicious.

For study purposes, the prostate is divided into four regions: RIGHT CENTRAL, RIGHT PERIPHERAL, LEFT CENTRAL and LEFT PERIPHERAL. Patients must meet the original entry criteria on this repeat mapping biopsy and have unilateral prostate cancer. If the patients meet the mapping-biopsy enrollment criteria, they are treated with **focal bipolar radiofrequency ablation (RFA)** meaning RFA of the sites where the biopsies were positive but no more than one prostate side. Efficacy is defined as negative biopsy cores at the sites of the focal ablation on repeat extended biopsies at 6 months after RFA. A second MRI will be performed just prior to the 6 month repeat saturation biopsy performed identical to the original pre-treatment biopsy.

At baseline (prior to pre-treatment biopsy) and at 6 months (prior to the repeat biopsy used to define efficacy) the patient will complete an American Urologic Association lower urinary tract symptom score assessment (AUA score), Rectal Assessment Scale (RAS), International Index of Erectile Function (IIEF-5), and the EPIC quality of life questionnaires.

Following completion of the focal prostate radio-frequency ablation study at 6 months from treatment, patients will undergo standard/routine care including serum PSA level every 6 months and as needed digital rectal examinations; any future prostate biopsies will be performed at the discretion of the treating physician.

Patients will also be required to complete a medical resource utilization (MRU) form to capture resource utilization between study visits, which can be used to estimate costs associated with procedure related complications and health care visits. Patients will be requested to complete a weekly diary of medical resource utilization to limit recall bias that may occur between study visits.

SCHEMA

SCHEDULE OF EVALUATIONS / STUDY CALENDAR

Parameter	Prestudy	Week 0	Week 6	3 months	6 months	End of Study Visit
History	X					
Physical examination including DRE	X		X	X	X	
QOL questionnaires (EPIC,IIEF,AUA,RAS)	X				X	
MRU (Recording weekly by patients; collected at the following visits by study coordinator)			X	X	X	
Toxicity assessment			X	X	X	
ECOG Performance Status	X				X	
Laboratory Investigations						
PSA	X		X	X	X	
CBC, differential, platelet count	X				X	
Serum Chemistries (must include, bilirubin, Alk Phos, ALT and AST)	X				X	
Glucose and Electrolytes (Na, K, Cl, CO ₂), BUN, Creatinine	X				X	
PT /PTT /INR	X				X	
U/A	X				X	
EKG	X				X	
Imaging Studies						
Chest X-Ray	X				X	
MRI and Mapping Biopsy	X				X	
Procedures						
RFA		X				
Discussion of final biopsy result and assessment of AEs						X

1.0 OBJECTIVES AND SCIENTIFIC AIMS

Primary Objective: To assess the local oncologic efficacy of focal RFA in men with unilateral, clinically localized prostate cancer as measured by the ability to obtain all negative biopsy cores at the sites of focal ablation of the cancer, “all negative” means no prostate cancer; if the biopsy contains inflammation, or pre-cancerous changes (high-grade prostatic intraepithelial neoplasia and /or atypical small acinar proliferation it will be considered negative for study purposes).

Secondary Objective: To evaluate the safety of the procedure and change in quality-of-life indicators from baseline to 6 months following focal RFA in patients with localized

prostate cancer. To understand and evaluate imaging characteristics of treated prostate cancer by bipolar RFA.

Tertiary Objective: To assess the potential health economic impact of focal RFA based on medical resource utilization data.

BACKGROUND AND RATIONALE

Epidemiological data demonstrate a marked increase in the number of men diagnosed with prostate cancer, and a profound migration towards earlier stage disease at the time of diagnosis. Implementation of large-scale serum prostate-specific antigen (PSA) screening programs and more extensive biopsy strategies are largely responsible for the increase in diagnosis. An analysis of the control group in the Prostate Cancer Prevention Trial illustrates the potential for extensive biopsy to result in over -diagnosis, of prostate cancer (Thompson et al.2004). Among 2,950 men with negative digital rectal examination (DRE) and PSA levels <4.0ng/ml, 15.2% harbored prostate cancer by biopsy, as did 6.2% of men with PSA levels<1.5ng/ml. In an era of increasing prostate cancer incidence and stage migration towards earlier disease, appropriate management of the disease requires assessment of risk; how likely is a given man's cancer to progress or metastasize over his remaining lifetime? What is the probability of success with treatment? What are the risks of side effects and complications with each treatment? Prostate cancer is relatively slow growing, with doubling times for local tumors estimated at 2 to 4 years. Some prostate cancers prove to be so small, low-grade, and noninvasive that they appear to pose little risk to the life or health of the host. A recent review of radical prostatectomy series suggest that 25-30% of men undergoing radical prostatectomy have pathologic features in the radical prostatectomy specimen consistent with an insignificant or "indolent" cancer that posed little threat to life or health (organ-confined cancer < 0.5cc, no Gleason grade 4 or 5 component). However, the biological potential of histologically detectable cancers is difficult to characterize with certainty, and a traditional 10 to 12 core transrectal prostate biopsy may underestimate the extent of cancer in the prostate in up to 50% of men with low-risk cancer. With alternative risk-assessment strategies (including extended or mapping prostate biopsies) some men have focal cancers that would not warrant complete gland treatment with radical prostatectomy, brachytherapy or external beam radiation therapy. While deferring definitive therapy (active surveillance) until progression of disease is an option in patients with low-risk and some with intermediate cancer, some men with a diagnosis of "cancer" do not accept this approach. As such there appears to be a role for therapy solely targeting the cancer (focal therapy; the male "lumpectomy"). This has the theoretical advantage of treating/curing the cancer while at the same time having fewer side effects than traditional whole-gland treatments.

The mechanism of action of bipolar RFA is complex. It has been proposed that RFA exerts its efficacious effect by: (1) the induction of protein denaturation by thermocoagulation (2) the rupture of cell membranes from heating, (3) the transfer of water from intracellular to extracellular spaces, (4) vascular stasis, and (5) the induced apoptosis. The introduction of ultrasound guidance and the bi-polar design of the probe, allowed the heating process to be controlled and monitored in real time.

PRIMARY OBJECTIVE

This protocol will investigate the role of focal bipolar RFA in a defined prostate cancer population examining treatment efficacy (elimination of the cancer) based on repeat biopsy at six months from treatment.

SECONDARY OBJECTIVES

1. Changes from baseline in quality-of-life.
2. Image characteristics of treated prostate cancer by bipolar RFA
3. To evaluate the safety of the procedure

TERTIARY OBJECTIVE: Evaluate the health economic impact of focal RFA.

OVERVIEW OF STUDY DESIGN/INTERVENTION

1.1 Design

This is a pilot study examining the efficacy (primary endpoint) and quality-of-life changes, safety, and image characteristics by MRI (secondary endpoint) in men with unilateral prostate cancer treated with focal RFA. In addition, the study will collect medical resource utilization data to assess the health economic impact of focal RFA (tertiary endpoint). We estimated the negative biopsy rate at 6 months after focal bipolar RFA is greater than or equal to 90%.

1.2 Intervention

Before any study procedures are performed (which includes all screening procedures, pre-treatment, treatment/intervention procedures, etc.), all patients will be asked to sign an informed consent form.

Eligible patients will have been diagnosed with unilateral prostate cancer, with PSA <10, Gleason score 6 or 7, up to clinical stage T2a, and prostate volume<60 cc. At enrollment, patients will undergo 1.5T MRI with DCE and DWI imaging. The prostate is divided into four regions: RIGHT CENTRAL, RIGHT PERIPHERAL, LEFT CENTRAL and LEFT PERIPHERAL. Then they will undergo a pre-treatment transrectal mapping prostate biopsy as currently performed at our institution. This procedure is performed under general anesthesia as an outpatient procedure. For study purposes, the prostate biopsy cores will be obtained from four regions: RIGHT CENTRAL, RIGHT PERIPHERAL, LEFT CENTRAL and LEFT PERIPHERAL. For patients to be eligible for treatment with focal bipolar RFA under this protocol they must meet the original entry criteria on this pre-treatment mapping biopsy.

Those men meeting the mapping-biopsy criteria will subsequently be treated with focal bipolar RFA. Treatment is performed under general anesthesia and will include the regions of the prostate containing cancer based on the mapping biopsy. If there are multiple unilateral areas of the prostate involved with cancer, a hemi-ablation will be

performed. This is an outpatient procedure, that takes between 1 and 2 hours, with the patient arriving 1-2 hours prior to the procedure and remaining in the recovery room for 1-2 hours after the procedure. The patient is given a voiding trial. If the patient fails same day voiding trial a Foley catheter will be placed with a second trial performed approximately one week after treatment. Clinical follow-up visits will be scheduled at 6 weeks, 3 months, and 6 months after focal bipolar RFA at which time a digital rectal examination and PSA test will be performed. These follow-up visits and procedures are part of this study protocol.

The primary endpoint of the trial is assessed at 6 months after focal bipolar RFA by repeat MRI imaging and post treatment mapping biopsy performed the same as pre-treatment. Treatment efficacy, defined as all negative biopsy cores at the site of the focal ablation, will be determined by the results of this mapping biopsy that will include complete biopsy of all regions of the prostate. Secondary endpoints will be evaluated through the standard quality-of-life questionnaires. For those patients not enrolled on this study protocol, their data from completion of the quality-of-life questionnaires will not be included in this investigation. Any adverse events that occur as a result of this study will be recorded and reported to the regulatory committees at Moffitt and IRB.

If after the mapping biopsy the patient does not meet the criteria for focal RFA, he will be excluded from this study protocol but considered and offered other management options for prostate cancer including active surveillance, radical prostatectomy or radiation therapy.

Stopping rules:

Criteria for stopping the Study:

1. If at the second mapping biopsy done at 6 months, more than 4 patients have a positive biopsy in the ablated area, the study will be stopped. This is based on the current treatment failure rate of 20% for radical prostatectomy.
2. If even one patient develops hematuria after the procedure requiring a second procedure to be performed, the study will be terminated.
3. If even one patient requires a Foley catheter for greater than 2 weeks following the procedure, the study will be terminated.
4. If even one patient develops an infection requiring inpatient hospitalization, the study will be terminated.
5. If even one patient develops a rectal fistula the study will be terminated.

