7.0 EVALUATION DURING TREATMENT/INTERVENTION

Before any study procedures are performed (which includes all screening procedures, pre-treatment, treatment/intervention procedures, etc.), all patients will be asked to sign an informed consent form.

Focal bipolar RFA will be done (after 4 weeks and no more than 12 weeks of initial mapping biopsy): a separate informed consent for this procedure will be obtained (which is separate from the informed consent to participate in the study), per the Cancer Center's policy for any procedure conducted for treatment/diagnosis. If the laboratory studies obtained at the pre-mapping biopsy assessment are still valid (within 6 months), they will not be repeated.

Six weeks after focal bipolar RFA; DRE, PSA, assessment of toxicity will be done. Toxicity of transperineal prostate biopsy includes bleeding, infection, urinary retention. Toxicity of focal bipolar RFA includes bleeding, infection, urinary incontinence, urinary retention, erectile dysfunction, urinary urgency, urinary frequency and rectal fistula.

Three months after focal RFA; DRE, PSA, assessment of toxicity will be done as mentioned in the preceding paragraph.

Six months after focal bipolar RFA; DRE, PSA, QOL questionnaire, assessment of toxicity; obtain serum electrolytes, UA, EKG and chest x-ray in preparation for repeat mapping biopsy to be done. The patient will be scheduled for the second MRI imaging and transrectal-guided mapping prostate biopsy # 2 to be completed within 6-8 months after focal bipolar RFA. After a biopsy is requested we will have a patient follow up in 1-2 weeks for discussion of results and assessment of any adverse events (this will be the end of study visit).

Patients will record weekly medical resource utilization data to share with their study coordinator at routine scheduled visits.

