APPENDIX E

 ID: _____ - _____
 Site _____ Subject _____

 INITIALS: _____
 F _____ M _____ L _____

Medical Resource Utilization Patient Diary
Patient Instructions:

Please complete the form below weekly by providing detail on non-study related health care visits. If there were multiple visits within a single week, please list out each individual visit.

Date	Did you have a health care visit this week (Y/N)?	If yes, how many healthcare visits did you have this week, and where did you visit?	For each of the visits, who did you see during this visit? (e.g., nurse, physician assistant, or physician)	What was the primary reason for this visit?	Did the healthcare personnel say the visit was related to the RFA procedure ¹ (Y/N)?	What treatment did you receive during this visit, if any?
Week 1:						
Week 2:						
Week 3:						
Week 4:						
Week 5:						
Week 6:						
Week 7:						
Week 8:						
Week 9:						
Week 10:						
Week 11:						
Week 12:						

1. Note to MCC clinical coordinator: If the patient's response to this question is "Y" an AE form must also be completed.

ID: _____ - _____
Site _____INITIALS: _____
F _____ M _____ L _____

Medical Resource Utilization Patient Diary

Patient Instructions:

Please complete the form below weekly by providing detail on non-study related health care visits. If there were multiple visits within a single week, please list out each individual visit.

Date	Did you have a health care visit this week (Y/N)?	If yes, how many healthcare visits did you have this week, and where did you visit?	For each of the visits, who did you see during this visit? (e.g., nurse, physician assistant, or physician)	What was the primary reason for this visit?	Did the healthcare personnel say the visit was related to the RFA procedure ¹ (Y/N)?	What treatment did you receive during this visit, if any?
Week 13:						
Week 14:						
Week 15:						
Week 16:						
Week 17:						
Week 18:						
Week 19:						
Week 20:						
Week 21:						
Week 22:						
Week 23:						
Week 24:						

1. Note to MCC clinical coordinator: If the patient's response to this question is "Y" an AE form must also be completed.

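### Two one-case stopping rules rely on unsolicited reports until week 6, the first toxicity assessment scheduled for every treated man

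*Combined protocol and SAP*

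**What the plan says.** The stopping rules in section 1.2 include two that act on a single early complication: "If even one patient develops an infection requiring inpatient hospitalization, the study will be terminated", and "If even one patient develops hematuria after the procedure requiring a second procedure to be performed, the study will be terminated". The same section describes an outpatient procedure with 1 to 2 hours in recovery, and sets clinic visits at 6 weeks, 3 months and 6 months.

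Section 7.0 gives the first safety check: "Six weeks after focal bipolar RFA; DRE, PSA, assessment of toxicity will be done". The study calendar agrees. Its toxicity row is first marked at week 6, and its week 0 column holds only the RFA. The one planned contact before that is a second voiding trial at about one week, for men who fail the trial on the day of treatment (section 1.2).

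Men also keep a weekly resource-use diary: "Please complete the form below weekly by providing detail on non-study related health care visits" (Appendix E). If a visit was said to be related to the RFA, a footnote tells the coordinator that "an AE form must also be completed". The calendar entry reads "MRU (Recording weekly by patients; collected at the following visits by study coordinator", with week 6 the first visit marked. Section 7.0 says the same: "Patients will record weekly medical resource utilization data to share with their study coordinator at routine scheduled visits".

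Other provisions deal with safety in general. Section 1.2 requires adverse events resulting from the study to be recorded and reported. Section 8.0 gives the principal investigator responsibility for safety, and provides for a monitor, team meetings at least monthly, and an interim analysis at 50% accrual or 10 patients. Sections 8.2 and 8.3 cover reports to the IRB and the Protocol Monitoring Committee.

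**The concern.** A rule that stops on one case protects the next man only if the case is known before he is treated. Section 7.0 lists bleeding and infection as toxicities of the RFA, and either could plausibly appear within days, when the man is at home. If he is admitted to another hospital, he may note it in his diary that week, but the coordinator is not due to see the page until week 6.

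The recording, review and reporting duties act on events that someone already knows about; none of them is a contact with the patient. Between the procedure and week 6, learning of care given elsewhere depends on the man or the outside provider coming forward. At stake is the number of further men ablated after a stopping criterion has been met.

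**Working it through.** The plan gives no figure for time to detection, so there is none to reproduce. The size below follows from its schedule and its accrual rate.

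**Inputs from the documents.** First scheduled assessment for all treated men: week 6, or day 42 (section 7.0, calendar). Accrual: 4 a month. Sample size: 20 (both section 11.2).

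**Assumptions.**
- The event occurs on day 3. The documents give no onset times.
- RFA proceeds at the accrual rate. It could be slower, because section 1.2 says: "If after the mapping biopsy the patient does not meet the criteria for focal RFA, he will be excluded from this study protocol". No exclusion rate is given.
- As a slow case, 20 RFAs are spread evenly over 12 months. Section 11.2 expects the whole study to finish in a year, and the final biopsy comes 6 to 8 months after RFA, so this is slower than the plan intends.

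**Step 1. Days between treated men** (30.44 days a month).
- At 4 a month: 30.44 / 4 = 7.61 days.
- Slow case: 12 × 30.44 / 20 = 18.26 days.

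**Step 2. Upper bound: no report until day 42.** The delay is 42 − 3 = 39 days.
- At 4 a month: 39 / 7.61 = 5.12 further men.
- Slow case: 39 / 18.26 = 2.14 further men.

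**Step 3. Allow for the end of accrual.** If man *i* has the event, only 20 − *i* men remain. So take the smaller of the bound and 20 − *i*, and average over *i* = 1 to 20.
- At 4 a month: the first 14 men each contribute 5.12 and the last six contribute 5, 4, 3, 2, 1 and 0. (14 × 5.12 + 15) / 20 = 4.34.
- Slow case: the first 17 men each contribute 2.14 and the last three contribute 2, 1 and 0. (17 × 2.14 + 3) / 20 = 1.97.

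**Step 4. Allow for early reporting.** Suppose a share *p* of events goes unreported until day 42 and the rest are reported at once. The expected number, given an event, is *p* times the averaged bound. The documents give no *p*.

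| Assumed *p* | 4 a month | 20 in 12 months |
|---|---|---|
| 10% | 0.43 | 0.20 |
| 25% | 1.09 | 0.49 |
| 50% | 2.17 | 0.98 |

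**Step 5. Allow for the chance of an event (illustration only).** The documents give no event rate. If 2% of men had a stopping event of this kind, the chance of at least one among 20 is 1 − 0.98^20 = 33%. Over the whole study, 10% non-report then gives about 0.33 × 0.43 = 0.14 further men, and 50% gives about 0.33 × 2.17 = 0.72.

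**Step 6. Effect of calls on days 7 and 15.**
- If both are answered, an event up to day 15 waits at most 8 days: 8 / 7.61 = 1.05 men at 4 a month, or 8 / 18.26 = 0.44 in the slow case.
- If the first is missed, a day-3 event waits 12 days: 12 / 7.61 = 1.58, or 12 / 18.26 = 0.66.

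**The case against.** The strongest reply is that these two triggers depend least on scheduled questioning. An inpatient admission and a second procedure both bring the man into medical care and leave records, and most would probably reach the study team quickly. Consent pages were not available for review and may tell men to call. Section 1.2 also carries a duty to record and report adverse events that is not tied to visits. All of this stands, and it is why the expected effect is probably small. It does not supply a contact: a report prompted by consent advice is still started by the patient, and the duty to record applies once the event is known.

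It is also fair to say that the diary is mainly a resource-use tool. Its stated purpose is the tertiary, health-economic objective, and section 11 treats the adverse event form as a separate source. The Appendix E footnote is a cross-check between the two. A reader might infer that the diary is the plan's safety-detection system and that collecting it at week 6 disables that system. The documents do not support this. The diary matters here only because it, too, is not due to be seen before week 6.

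Two further inferences should be resisted. The first is that about five men would be ablated after a stopping event. That is an upper bound, which needs an event, complete silence until day 42 and RFA at the full accrual rate. The second is that the Background's figure of up to 50% gives the share excluded after the mapping biopsy. It concerns underestimated cancer extent on a 10 to 12 core biopsy, and men with several areas on one side remain eligible for hemi-ablation.

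**Conclusion.** The point holds as a gap in scheduled ascertainment. For the infection and hematuria rules, no contact with every treated man is planned before week 6, and the other safeguards do not create one. The catheter rule is not part of the point, because the one-week voiding trial largely covers it.

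Given an event, the averaged expectation at the stated pace runs from 0.4 to 2.2 further men for non-report between 10% and 50%, with 4.3 as the averaged ceiling. Slower treatment roughly halves these figures. The range rests on assumed non-report rates and an assumed day-3 onset; early onset is clinical inference. A reader might infer that the plan lets such events go undetected for six weeks. It does not say that: earlier reports are possible and likely. No trial result is invalidated. This is a low-cost safety improvement with a probably small expected effect.

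**What to change.** Keep the stopping criteria as they are, and make three additions.

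- **Contacts.** Enter in the calendar a coordinator telephone call to every treated man at about day 7, combined with the voiding trial where there is one, and another just after day 14. Ask about any admission, any further procedure for bleeding, catheter status and removal date, and other adverse events.
- **Check before each RFA.** Review the calls that have fallen due for men already treated. A documented attempt is enough, so one unreachable man does not block treatment. At 4 a month this covers about two men at a time (15 / 7.61 = 1.97).
- **Hold.** State that no further RFA is done once a stopping event is found.

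The cost is about 40 short calls (2 × 20) by the existing coordinator, one CRF page and two calendar entries, with no added visit, test or staff. There are two limits: an unanswered call gives no information, and events first arising between days 15 and 42 are not found any sooner.
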